4.2.2 Secondary Outcome Measures

Secondary outcomes include:

- Code status preferences (Aim 1)
- Use of palliative care consult/services (Aim 1)
- Hospice use (Aim 1)
- Health Care Proxy (Aim 1)

Secondary outcomes related to Aim 2a (patients 18+ years admitted to one of the study inpatient units with ADRD/delirium) include:

- Documentation of ACP Preferences in Electronic Health Record

Secondary outcomes related to Aim 2b (caregivers of patients with ADRD/Delirium) include:

- ACP knowledge (Aim 2)
- Confidence in future care (Aim 2)
- Communication satisfaction (Aim 2)
- Decisional satisfaction (Aim 2)
- Decisional conflict (Aim 2)

5 Study Design

This is pragmatic SW-CRT of a PCE-led, video-assisted COVID-19 ACP intervention in inpatient-based units (3 medical-surgical wards, Medical ICU, Cardiac ICU, Neurology ICU, step-down unit) at two hospitals: BMC and North Shore University Hospital (Northwell Health). All inpatients ≥ 65 and all patients with ADRD/Delirium ≥ 18 who are hospitalized on a unit during the intervention phase will receive the intervention.

This 2-year study (2 month data collection and tool preparation, staff training and site standardization (we are already embedded in both health systems doing similar work; thus this

short timeframe is feasible); 16 months rolling recruitment and surveying; 2 months data cleaning and analysis, and 4 months manuscript preparation and dissemination of findings) will roll out the intervention to 14 randomized inpatient units at 2 sites. Every two months, an additional inpatient unit will be added to our intervention at each hospital, i.e., there will be seven waves or "steps"; for a total of 7 units at each hospital.

Consistent with a SW-CRT with two hospital units per step (cluster), prior to the collection of any data in the pre-intervention period, we will generate a set of uniform random numbers for each of the seven clusters to be assigned to a starting period for the study intervention. There will be eight study periods in total with a usual care period at the start of the study for all clusters. The first randomized intervention period will then begin in period two.

Cluster	Baseline	14 Months of Clustered Intervention Expansion							
	M0	M2	M4	M6	M8	M10	M12	M14	
1									
2									
3									
4									
5									
6									
7									

The data needed to assess the outcomes for all patients will be derived from each hospital's EHR (Aim 1).

For Aim 2b, 600 caregivers of patients with ADRD/Delirium (300 control phase; 300 intervention phase) will be surveyed by telephone during (or within one week of) the index hospitalization to assess caregiver-centered outcomes.

Each day PCEs, who will be nurses or social workers on the palliative care team, will approach patients who are currently hospitalized under Aim 1 or Aim 2a. The PCE will then proactively use the goals-of-care video decision aid (or any of the additional videos regarding CPR, hospice, dementia, etc., as relevant and in the appropriate language) to provide educational support and assist in delivering primary palliative care services relating to goals-of-care conversations and ACP documentation. The videos range from 4-6 minutes in length and the PCE will watch the videos together with the patient and caregiver on an iPad (or remotely via telehealth with the caregiver).(130)

The PCE will arrange all video showings to include patient and caregiver (when possible and acceptable to the patient); when patients are unable to view a video (e.g., loss of capacity, delirium), the caregiver will view the video. The videos do not replace clinician counseling; indeed, they are designed to allow the PCE to confirm comprehension and to stimulate

conversation with a shared vocabulary. The PCE will then communicate the patient's or caregiver's wishes to the treating primary medical team to coordinate care.

In cases when the PCE deems that engagement with the full palliative care team is warranted, they will approach the treating primary medical team to place the consult. If/when the PCE exhausts the automated list for patients, they will coordinate with the palliative care consult team to select patients from the list of requested consultations. The PCE role will be fully integrated into existing hospital practices at our sites consistent with the pragmatic nature of this study design.

For Aim 1, the study population will consist of patients 65 years or older who are admitted to one of the study inpatient units in the hospital. For Aim 2a, the study population will consist of any patient ≥ 18 years admitted to one of the study inpatient units in the hospital with a diagnosis of ADRD/Delirium. For Aim 2b, the study population will consist of adult (≥ 18) caregivers of patients identified in Aim 2a. These caregivers will be recruited to complete a phone survey for our secondary caregiver outcomes

The data needed to assess the outcomes for all patients aged 65 or over will be derived from each hospital's EHR (Aim 1). For Aim 2, 600 caregivers (300 control phase; 300 intervention phase) will be surveyed in-person (or remotely) during the index hospitalization to assess caregiver-centered outcomes.

6 Potential Risks and Benefits

6.1 Risks

The potential risks are minimal given the fact that the intervention promotes learning about medical care for patients, improves communication for patients and their families regarding advance care planning and self-determination, and the concordance between patient's wishes and the care they receive.

The major potential risk for subjects is loss of confidentiality. Loss of confidentiality is very unlikely because specific procedures have been implemented by the research team to prevent such disclosure and these measures will be maintained during the proposed study. Another risk in Aim 1 is being upset by the intervention videos/questions. Probability of this occurrence is minimal. We have conducted a series of clinical trials for patients with advanced illnesses and have rarely had patients get upset due to the topic. In each of these cases, the participant was interested in continuing after a short break.

For subjects enrolled in Aim 2, there is a risk that they could become upset or saddened by some of the survey questions.

6.2 Potential Benefits

This study provides no direct benefit to subjects, however there is the potential for patients and clinicians in the clinics to benefit from the study by having their treatments better aligned with their preferences.

6.3 Analysis of Risks in Relation to Benefits

The minor risks for the participants in this study may be considered counterbalanced by the potential direct benefits and knowledge gained. The results gleaned from the study are intended to improve the ACP of the overall inpatient population, and particularly those with ADRD/Delirium. Thus, the risk/benefit balance for this study appears favorable.

7 Study Subject Selection

7.1 Subject Inclusion Criteria

Over the two years of the trial, we will examine data on approximately 15,000 patients ≥ 65 admitted to these 23* units for our primary and secondary outcomes (Aim 1). Given the pragmatic nature of this trial, our inclusion criteria are quite broad and consistent with the goal of pragmatic trials.

We will also survey caregivers of 600 patients with ADRD/Delirium to conduct a telephone administered survey for caregiver-centered outcomes (knowledge, confidence, communication satisfaction, decisional satisfaction, and decisional conflict) during the index hospitalization. Caregivers may or may not be designated as ADRD/Delirium legal surrogate decision maker for the patient (i.e., most patients with ADRD/Delirium do not have a legally designated representative.) Any adult identified in the EHR as the contact family member or friend will be eligible to partake in the caregiver survey. Half of surveys will be conducted during the control period; half during the intervention period. Caregivers will be either English- or Spanish-speaking adults, which are the languages in which our surveys are validated. For patients in the control group, surveys will be completed during the hospital stay or within 1 week of discharge. For patients in the intervention group, the survey will be completed AFTER the PCE intervention, and up to 1 week after discharge.

*14 units (7 per hospital) will be included in the stepped wedge trial, an additional 9 units (3 at BMC and 6 at NorthShore) will be used to recruit additional control participants only. These additional units were added due to low recruitment at the start of the study and the decreasing number of control units as the stepped wedge design progresses. The target enrollment of 600 caregivers is still accurate.

Adding delirium to the list of eligible diagnoses will also increase the potential number of eligible subjects. The surveys are applicable to the caregiver of any patient who is not capable of making their own health decisions; this includes patients who are experiencing any sort of memory or cognitive decline.

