4.1 Study Objectives

The **overall objective** of this study is to reduce the burden of COVID-19 by expanding the reach of inpatient palliative care services, especially for patients with ADRD/Delirium. We propose to conduct a stepped wedge cluster randomized trial (SW-CRT) of a PCE video intervention among hospitalized patients aged 65 and over, or any patient ≥ 18 years with ADRD/Delirium and their caregivers in the ward and ICU settings of two major hospitals: Boston Medical Center (BMC) and North Shore University Hospital. Patient outcomes will be abstracted from electronic health records with Natural Language Processing (NLP).

We will test our hypotheses via the following **Specific Aims**:

Aim 1: To test the effects of a PCE video intervention leveraging video decision aids on the quality of end-of-life care. We will conduct a SW-CRT to evaluate intervention effectiveness by comparing the following outcomes among 9,000 hospitalized patients: ACP documentation; preferences for resuscitation; palliative care consults; and, hospice use. **Hypotheses:** *A higher proportion of patients in the intervention phase (vs. control) will: (1) complete advance care plans (primary outcome), (2) have documented resuscitation preferences, (3) have palliative care consults, (4) enroll in hospice over the course of one year of follow-up, and (5) have documented health care proxies.*

Aim 2a: The manual chart review activity is intended only for the patients whose caregiver participated in the survey activity. It is distinctive from the NLP activities described in our protocol which identify ACP documentation from the free-text of clinical notes. The chart review will involve a thorough human review of structured ACP elements such as DNR/DNI order, MOLST/POLST and Health Care Proxy form completion in each patient's chart.

Aim 2b: To characterize caregiver-centered outcomes of patients with ADRD/Delirium, including: (1) knowledge, (2) confidence in future care, (3) communication satisfaction, (4) decisional satisfaction, and (5) decisional conflict in 600 caregivers of patients with ADRD/Delirium admitted to the hospital. **Hypothesis:** *Intervention phase caregivers of patients with ADRD/Delirium (vs. control) will have higher knowledge, confidence, communication satisfaction, decisional satisfaction, and lower decisional conflict.*

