12.2 Sample Size Determination

Statistical power and sample size: All sample size estimates here assume a minimum of 80% power and a two-sided alpha of 0.05. We employ the method for the computation of sample size for cross-sectional stepped wedge studies comparing intervention to usual care in two-group statistical analyses. This method incorporates information on the number of steps used in the

stepped wedge/cluster randomized design, the number of subjects per time period, and the degree of clustering via the intraclass correlation coefficient (ICC) to compute the design effect, the factor by which the sample size found to provide sufficient statistical power for a meaningful intervention difference in outcome assuming independent data is multiplied. For the primary outcome of the documentation of ACP in the medical record, a sample size of 440 records per group in a chi-squared test for independent data will provide 80% power at a two-sided alpha of 0.05 to detect a difference in the proportion of subjects with notation of 35% in the intervention group compared to 25% in the usual care group, values consistent with prior research and expectation based on clinical data from the two health systems estimated from recent data. Based on our planned number of steps (7 with one uniformly applied usual care period across all hospital units), enrollment per study period, and a reasonable ICC of 0.01, the design effect is 2.72. Thus, we will need to obtain outcome data from the records of at least 2394 subjects overall (1197 per health system) to provide 80% power for our analysis of intervention effectiveness. We anticipate, however, that as many as 15,000 records will be available for analysis with respect to the documentation of ACP. Thus, our planned sample size for our primary records-based analysis on 15,000 records will therefore provide more than adequate power to test for differences in our primary outcome.

Data for Aim 1 is derived from the EHR and as is typical for trials that integrate new initiatives within the workflow of large institutions in a SW-CRT that does not involve consent. Indeed, we have been previously approved by multiple IRBs for such activities. Along with our exceedingly efficient NLP-assisted and human-confirmed software method for EHR data extraction, we can have a very large study sample with for this activity.

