distributions of the uncertainty and knowledge scale scores, the outcomes of interest between intervention and usual care subjects, as well as the distributional characteristics of all other salient study variables. We will generate descriptive statistics (means, standard deviations, quantiles for continuous variables; counts and percentages for categorical variables) and schematic plots (box-and-whisker, quantile-quantile plots). Given the nature of the cluster randomization that we will employ, we will utilize statistical analytic methods that take the correlated nature of the data into account as well as the influence of time to account for secular trends. In this study, we will examine both the health system and hospital unit as clustering variables, with the hospital unit as the primary clustering variable. We will compare the intervention and usual care groups on salient variables in order to assess balance in the distributions of these variables. Variables found to differ between the study groups will be further evaluated to assess their confounding effects of intervention vs. usual care differences on outcomes in multivariable analyses for correlated (clustered) data.

Aim 1. To test the combined effects of a COVID-19 ACP Educator-led, video-assisted palliative care intervention on rates of: ACP documentation; Medical orders for resuscitation preferences in the EHR; Palliative Care Consults; and, Hospice use. ***Hypothesis: A higher proportion of patients in the intervention phase (vs. control) will: complete ACP documentation (primary trial outcome), have documented orders for resuscitation preferences, have palliative care consults, and enroll in hospice.***

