Primary outcome: ACP documentation. In order to formally estimate and test differences in the proportion of patients with documentation of ACP between the intervention and usual care groups, we will employ logistic regression models for correlated binary outcome data. These models will either involve the use of robust variance methods to account for the clustering of these data by hospital site and/or health system via generalized estimating equations (GEE) or the inclusion of a random effects terms (in which case, the results will be interpreted as cluster-specific). Other potential modifiers of the effect of intervention, confounding variables, or covariates can be added to this model as fixed effects. Although we do not expect effect modification in the study data, we will examine the potential for such effects (interaction) through the use of stratified analyses and the inclusion of interaction terms with study group in our statistical models. Candidate effect modifiers will be specified a priori and will include age, gender, race/ethnicity, religion, and language. We will also examine and incorporate secular trend effects, i.e., the effect of time over the course of the study. Statistically significant interactions with the intervention will be retained and the nature of heterogeneous intervention effects will be estimated using the interaction model.

Based on our prior work in which we exhibited the fact that African-American and Hispanic patients are at particularly high risk for lower level of knowledge related to ACP, not discussing ACP with family, not having a health care proxy, and not having ACP documentation, we anticipate that this intervention may be particularly beneficial for African-American and Hispanic patients.(115, 131, 132) Accordingly, we will evaluate heterogeneous treatment effects by race and ethnicity and anticipate having adequate diversity in our study population to make such assessments. All data regarding Aim 1 will come from the EHR. Our institutions maintain excellent self-report information regarding race and ethnicity.

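### Section 7.1 counts nine later-added, control-only units in the Aim 1 outcomes, and section 12.3 neither excludes nor models them; the exposure is mainly in the caregiver outcomes.

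*Combined protocol and SAP*

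**What the plan says.** Section 5 states that the study "will roll out the intervention to 14 randomized inpatient units at 2 sites", seven per hospital, over eight periods. By the last period every one of these units is in the intervention phase.

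Section 7.1 uses a larger set for the record-based outcomes: "we will examine data on approximately 15,000 patients ≥ 65 admitted to these 23* units for our primary and secondary outcomes (Aim 1"). The asterisk leads to a footnote that puts 14 units in the stepped wedge and adds that "an additional 9 units (3 at BMC and 6 at NorthShore) will be used to recruit additional control participants only". It describes them as "added due to low recruitment at the start of the study and the decreasing number of control units as the stepped wedge design progresses", and then confirms the target of 600 caregivers.

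The record counts differ between sections. Section 4.1 describes "comparing the following outcomes among 9,000 hospitalized patients", while section 12.2 refers to "our planned sample size for our primary records-based analysis on 15,000 records", the count that section 7.1 attaches to 23 units.

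Section 12.3 specifies GEE or random effects "with the hospital unit as the primary clustering variable", with health system also examined and an adjustment for time. It provides for balance checks, says that "confounding variables, or covariates can be added to this model as fixed effects", and adjusts Aim 2b for calendar time and imbalanced caregiver characteristics. It applies the record-based analyses to all Aim 1 and Aim 2a patients. It contains no restriction to the 14 units, no term for the nine and no analysis without them.

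**The concern.** The nine units were not randomised, were chosen after launch and never cross over. GEE and random-effects models both draw on comparisons between units. If the nine differ systematically from the 14, part of that difference therefore passes into the estimated treatment effect without the protection of randomisation. The clustering terms address correlation, and the time terms address a shared trend. Neither removes a level difference between the two kinds of unit. The balance checks cover measured variables and do not name unit type.

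The secondary caregiver outcomes of Aim 2b are most exposed, because the footnote's purpose is to recruit controls. The Aim 2a chart review follows the same patients, so it inherits the issue. For the primary outcome, the analysis set (14 or 23 units) is not stated consistently and could be settled after the data are seen.

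**Working it through.** **Unit count (sections 5 and 7.1).** 7 x 2 = 14 randomised units; 3 + 6 = 9 added units; 14 + 9 = 23. The plan's figure reproduces.

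**Control unit-periods.** With two units crossing per step, 14 - 2(p - 1) randomised units are controls in period p. Over eight periods this gives 14 + 12 + ... + 0 = 56 control and 56 intervention unit-periods. The share of control unit-periods held by the nine is 9/(9 + 14 - 2(p - 1)): 9/17 = 53% in period 4, 9/11 = 82% in period 7 and 9/9 = 100% in period 8. These are shares of unit-periods, not of caregivers.

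**Model.** Unit-period mean = period effect + treatment effect + random unit intercept + error. A cell of n subjects has variance ICC + (1 - ICC)/n, and two cells of the same unit have covariance ICC. The treatment estimate is a weighted sum of cell means, with weights from the treatment row of (X'V⁻¹X)⁻¹X'V⁻¹. The sum of the weights on the nine units' cells is the share of a constant nine-versus-14 difference that leaks in. It is negative: if the nine score higher, the effect is understated. Absolute values are given below.

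**Aim 2b inputs.** From the plan: 300 control and 300 intervention caregivers, and ICC 0.01. Assumed: ICC up to 0.05, equal units, the nine joining in period 4 (9 x 5 = 45 unit-periods), and X control caregivers from the nine. Cell sizes are 300/56 for intervention, (300 - X)/56 for randomised control and X/45 for the nine. X = 134 corresponds to equal yield per control unit-period: 300 x 45/(56 + 45) = 133.7.

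| X | Leak, ICC 0.01 / 0.05 | Type I error if the difference is 0.2 SD (assumed), ICC 0.01 / 0.05 |
|---|---|---|
| 20 | 0.161 / 0.173 | 6.0% / 6.0% |
| 60 | 0.368 / 0.340 | 11.1% / 9.3% |
| 134 | 0.589 / 0.494 | 23.6% / 14.7% |

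Entry in period 2 instead gives 0.135 / 0.145, 0.330 / 0.298 and 0.568 / 0.450. Letting unit sizes vary (assumed CV 0.5) gives 95% ranges, across both ICCs, of 15-18%, 32-40% and 47-61%. Adding a hospital term moves the X = 134, ICC 0.01 value only from 0.589 to 0.583.

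**Aim 1, only if the nine were pooled** (15,000 records, equal units):

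| Entry of the nine | Random intercept, ICC 0.01 / 0.05 | GEE, independence weights |
|---|---|---|
| Period 1 | 0.180 / 0.044 | 0.692 |
| Period 4 | 0.252 / 0.069 | 0.629 |

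Section 12.3 allows either model and names no working correlation. For an assumed 5-point difference, the shift runs from 5 x 0.044 = 0.2 to 5 x 0.692 = 3.5 points, against the 10-point benchmark in section 12.2.

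**Precision under a remedy.** Aim 1 on 14 units at 80% power, ICC 0.01 and mean proportion 0.30 detects 4.5 points (9,000 records), 5.9 (5,000) or 8.1 (2,394, the plan's own minimum: 2 x 440 x 2.72 = 2,393.6). For Aim 2b at 90% power and ICC 0.01, the detectable effects in SD are:

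| X | No term | Indicator for the nine | 14 units only |
|---|---|---|---|
| 20 | 0.355 | 0.378 | 0.380 |
| 60 | 0.331 | 0.389 | 0.394 |
| 134 | 0.308 | 0.424 | 0.433 |
| 240 | 0.299 | 0.585 | 0.593 |

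The indicator reduces the leak of a constant difference to zero. Unit fixed effects do so too, at 0.47-0.52 SD for X from 20 to 134.

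**The case against.** The strongest reply concerns Aim 1. Sections 4.1 and 12.1 define it as the stepped-wedge comparison, and the footnote puts 14 units in that wedge. Aim 1 takes its data from records under a consent waiver and expects far more than the 2,394 records needed, so it had no recruitment shortfall to repair. On that reading the nine serve the survey alone. This stands as the more plausible intent, and it reduces the Aim 1 part to a sentence that conflicts with its own footnote. It does not remove the conflict, because section 12.3 never states the restriction.

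A reader might infer that the primary analysis will pool all 23 units, or that 15,000 x 14/23 = 9,130, being close to 9,000, shows where the two counts come from. The documents support neither inference: they do not explain the two counts or link them to the unit sets.

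The second reply is that every size rests on assumptions. This also stands. If the nine were exchangeable with the 14 at ICC 0.01, the difference in their means would have SD sqrt(0.01 x (1/9 + 1/14)) = 0.043, and the typical bias would be only 0.01-0.03 SD. A 0.2 SD difference would have to be systematic, and nothing in the documents shows one.

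A third reply is that a hospital term would absorb the 3/6 against 7/7 mix. The check above shows that it barely changes the leak. Finally, protection costs precision, so choosing the main Aim 2b model is a genuine trade-off between bias and precision.

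**Conclusion.** The omission is certain; its consequence is not. The plan leaves nine non-randomised, never-treated units without a stated place in the analysis, and the specified models would not neutralise a systematic difference. For Aim 2b, between about one sixth and three fifths of any constant difference would enter the estimate, depending mainly on how many control caregivers come from the nine. That number, the joining date and the type of unit are not in the documents, so both the size and the direction of any bias are unknown. It would be wrong to conclude that the caregiver results are biased or that the primary outcome is compromised. For Aim 1 this is a scope conflict to reconcile. The leak of 4-25% (random intercept) or 63-69% (independence weights) applies only if the nine were in fact pooled. The point should be fixed before analysis.

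**What to change.** 1. Reconcile the 23-unit sentence in section 7.1 with its footnote. State in section 12.3 that the Aim 1 primary and secondary analyses use only the 14 randomised units, and restate the record count for those units in sections 4.1, 7.1, 12.1 and 12.2. The cost is wording: 14 units still detect 4.5-8.1 points with 9,000 down to 2,394 records, inside the 10-point benchmark.
2. For Aim 2b and the Aim 2a chart-review outcomes, pre-specify how the nine are handled. Report both the analysis of all units and one protected against a constant nine-versus-14 difference: either the 14 units only or an indicator for the nine. If the indicator is used, state that it assumes a common time trend in both sets. Label any estimate that relies on the nine without this protection as not fully randomised.
3. Report caregivers by period and unit type, so that readers can see how far the controls depend on the nine.

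The cost of item 2 is precision. With 20-134 controls from the nine, the indicator analysis detects 0.38-0.42 SD at 90% power, better than the 0.53 stated in section 12.2. If the nine supply 240, either protected analysis detects about 0.59 SD, worse than 0.53. Reporting both analyses makes that trade-off visible.
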